STELLA-FTD is a 36-week randomized controlled, repeated measures study. Embedded in it is an 8-week care partner behavior change intervention, delivered in a peer environment via videoconferencing technology. All interactions are completed by telephone, real-time videoconferencing, asynchronous website access and electronically-administered assessments. There are no in-person activities. Importantly, STELLA-FTD is administered via a telehealth platform, ensuring that it is *accessible* to any care partner with internet access, including underrepresented and rural families. All STELLA-FTD activities (e.g., screening, enrollment, intervention) will be managed by the Oregon Alzheimer's Disease Research Center (OADRC) team at OHSU. STELLA-FTD will be monitored by the OHSU IRB, adhering to the highest ethical and regulatory standards.

Rational for intervention study design. To test our hypotheses we will use a randomized controlled, two-group, repeated measures design (Figure 2). This design was chosen to maximize internal validity and address the shortcomings noted in the STELLA-FTD pilot that affected rigor: the quasi-experimental design, insufficient power and no examination of mechanism of action.

Two groups are needed in this intervention to test the mechanism of action and isolate the effect of ABC training. To do this, we designed the intervention so that both groups receive the matching "dose," of the foundational curriculum. The test group will receive the foundational curriculum *plus* ABC training. Comparing differences between the groups will allow us to assess the effect of ABC training (see **Intervention**).

We considered having a “standard care” group instead of the dose-matched group, but because the two groups would receive very different interventions, this would not inform us of the effect of ABC training and ultimately, the mechanism of action.

This design will allow us to assess the effect of the process variables (use of ABC planning, self-efficacy) on the primary outcome variable, care partner burden, while controlling for selection bias and diffusion of treatment ⁽³⁹⁾.

Rigor, bias and transparency. Unlike the quasi-experimental design used in our pilot, the repeated measures RCT described here will provide evidence for efficacy, allow isolation of the active components of the intervention and limit bias ⁽⁴⁰⁾. The study will be powered to identify the effect size of the intervention.

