We will employ multiple strategies to minimize threats to internal validity and mitigate bias. First, all enrolled care partners will be randomized to the test or control group of the intervention allowing for comparison between and within groups. Care partners will be blinded to group designation.

Second, to limit diffusion of information between the two groups there will be no study-driven opportunities for the test and control group care partners to interact. The telehealth modality uniquely allows for siloed training sessions that do not include in-person interactions (e.g., they will not meet in a hallway or waiting room). While both groups will have access to the STELLA-FTD website, there will not be a chat option to interact. We will engage separate interventionists and handbooks for each group. Nominal names for each group reduce the risk of valuing one group over the other ⁽³⁹⁾.

Third, we balanced the need for frequent testing with the possibility of re-test bias by designing multiple-week gaps between testing. To limit social bias, assessments of burden and other variables (see “Measures”) will be electronically delivered to each care partner’s email so they can complete them in the privacy of their homes. Staff members will not administer these assessments. Finally, careful adherence to fidelity practices (see **Fidelity**) will limit intervention drift from the protocol.

Our methods, protocol and findings will be transparent to the wider community. STELLA-FTD will be posted on the ClinicalTrials.gov website. We will publish our protocol, training and fidelity procedures and findings to promote reproducibility of the study. We will deliver our findings to the participants and other care partners to honor their contributions.

Sample size calculation/power analysis. A known weakness on the STELLA-FTD pilot was the small sample size. For the proposed study, we will engage a sample of care partners that will be large enough to identify statistically significant findings. To our knowledge, STELLA-FTD is the **first study of its kind** to test an ABC-type behavioral intervention with a large group of **FTD** family care partners. Thus, the power analysis for STELLA-FTD is hampered by the lack of larger-scale studies. We therefore calculated the power based on published ADRD behavioral research that used our primary outcome variable, reactivity on the RMBPC ^(2, 30, 41).

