In Teri et al. ⁽³⁰⁾ the differences in RMBPC reactivity scores ⁽²⁾ between baseline and post-intervention visit were -1.6(SD=7.6) with an effect size of 0.21 in care partners in the control group (routine medical care), and -5.8(SD=9.8) with an effect size of 0.59 in care partners in the intervention group (the ABC group). The effect size of difference in change in RMBPC ⁽²⁾ reactivity score between the two groups was 0.38. Based on this study, we conservatively determined the sample size calculation with an effect size of difference in pre-post intervention change as 0.3. To achieve at least 80% power to detect such a difference in a study design with three repeated measurements and an Intra-Class Correlation (ICC) =0.5 to 0.6 in compound symmetry covariance structure, we need at least 117 to 128 subjects/each group, for alpha = 0.05.

We anticipate an increase in power due to our conservative approach, e.g., based on three time repeated measures instead of 6 time points (Figure 2) and smaller effect size between intervention

and control groups on the RMBPC (compared to 0.59 Teri et al.)⁽³⁰⁾. We will use this increase in power to compensate for the complexity of the proposed model when adjusting covariates are taken into consideration. For self-efficacy, based on estimates from the STELLA-FTD pilot, group sample sizes of 128 will achieve 80% power to detect a difference of 0.32 at alpha level of 0.05, which is reasonable given pilot data trends⁽⁴²⁾.

In determining the sample size, we took attrition into account. Based on our experience⁽²⁹⁾, it is likely that up to 15% of the sample will withdraw due to schedule demands, illness and death, thus we will over-recruit to enroll 300 care partners.

5) Study Population

a) Number of Subjects

Participants. Informed by our power analysis, we will enroll a total sample of 600 participants: 300 family care partners and their 300 care recipients with FTD. For our study “family care partner” includes any person who is considered “family” to the person with FTD, such as direct relations, fictive kin, close friends and neighbors. “Care recipient” is defined as an individual with an FTD diagnosis: bv-FTD, PPA, progressive supranuclear palsy (PSP), corticobasal degeneration (CBD), or FTD with motor neuron disease⁽⁴³⁾.

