Please see Decisionally Impaired Adults Supplement for details of consenting persons with FTD.

6) Procedures

Enrollment and Set-up. After consenting to the study, Care Partners will be contacted by the study research assistants (RA) to collect enrollment information (e.g., demographics, contact information) and orient them to logging on to the STELLA-FTD on their computers (see “Technology” below). The RA’s will mail the “STELLA-FTD” Care Partner Handbook” and ClinCard to the Care Partner, which provides details about all study activities.

Randomization. Care partners will be randomized to either the test or control group (Figure 2) using an electronic randomization process and will be blinded to their group designation. The control group (“Comet”) will receive the basic STELLA-FTD curriculum, the test group (“Meteor”) will receive the basic curriculum *plus training in the ABC analytic approach.*

Interventionists. The STELLA-FTD intervention is provided by “guides,” health care professionals (e.g., Speech and Language Pathologists, nurses) with experience in dementia care. There will be two guides for each group per 8-week cohort, for both control and test (see “**Fidelity**,” for training information).

Technology. STELLA-FTD is a technology-based intervention. We have been conducting telehealth-based care partner research since 2016 ^(15, 24, 29, 31, 33, 34, 41, 42, 52) and our experience informs delivery of STELLA-FTD in a safe, acceptable manner. The intervention, assessments and all communications will be delivered by electronic, videoconference, or by telephone strategies. The consent form will explain technology and privacy risks.

Participant Communication. All contacts, surveys and interventions may be completed by phone, encrypted email, videoconferencing and/or electronically-administered assessments using REDCap or Qualtrics servers. All other study activities (screening, consenting, intervention and surveys) will be done at OHSU by OHSU scientists, interventionists and staff. There are no in-person research activities. We will send occasional newsletters with study updates use OHSU Marketing Cloud. The OHSU Marketing Cloud has been approved by the OHSU Director of Internal Communications, and there is a Business Associate Agreement in place for handling of PHI.

Care partners will have the option of opting out if they do not want to receive the newsletters.

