H1: Upon completion of the STELLA-FTD 8-week intervention, care partners in the test group will have significantly lower (better) burden scores than those in the control group. For H1, we will employ a mixed effects model to analyze whether the change in reactivity on the RMBPC (2) differs across groups (test vs. control) over the intervention period. Two fixed effects will be included in the model: 1) Group effect will be included as a dichotomous categorical variable (test vs. control); 2) Time effect will be included as a continuous variable. The interaction between group and time (group x time) will also be included. Random intercepts will be incorporated for subject specificity in the model to account for clustering effect within subject over time. We will perform a hypothesis test for the coefficient of the interaction term (group x time) to assess the difference in change on primary outcome in the intervention group as compared to control group, over time. We will extend the model to include diagnosis type (e.g., PPA, bv-FTD), frequency of behavioral symptoms as measured on the RMBPC (2), socio-demographic covariates (e.g. sex, age, sex, education) and external support group use. Results will be considered significant at $\alpha = 0.05$, with two-sided test. Similar analyses will occur at Week 20 and 36.

Aim 2. Test the mechanism of action of STELLA-FTD by isolating the ABC training component (the behavior change technique) and determining its relationship to self-efficacy (the intervention target) and burden (the primary outcome) (Figure A).

The statistical analyses for Aim 2 will be carried out in three steps to investigate the mediated effect of self-efficacy ⁽³⁾ on the association between intervention and primary outcome, the RMBPC ⁽²⁾ reactivity score.

H2: Care partners who receive STELLA-FTD with ABC training (the test group) will have significantly higher self-efficacy scores ⁽³⁾ than the control group. To test H2 in the first step, we will employ a similar mixed effect model as H1. The mixed effect model analyses will be performed on total self-efficacy score as the outcome. A hypothesis test for the coefficient of the interaction term (group x time) will be performed to assess the difference in change on self-efficacy score in the test group as compared to control group, over time.

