H3: Care partners with higher self-efficacy will have lower burden scores. In the second step to test for H3, we will construct a mixed effect model on the RMBPC ⁽²⁾ reactivity score as the outcome. Total self-efficacy score ⁽³⁾ will be included as a continuous independent variable; time will be included as a continuous variable. The interaction between total self-efficacy score and time (self-efficacy score x time) will also be included. Random intercepts will be incorporated for subject specificity in the model to account for clustering effect within subject over time. A hypothesis test for the coefficient of the interaction term (self-efficacy score x time) will be performed to assess the relationship between change on primary outcome (RMBPC reactivity score ⁽²⁾) and total self-efficacy score ⁽³⁾, over time.

H4: Self-efficacy will partially mediate the relationship between ABC training and burden. In the third step, a mixed effect model on RMBPC reactivity score ⁽²⁾ will be constructed based on the model in H1. We will extend the established model in H1 to include total self-efficacy score as a continuous covariate and the interaction term between total self-efficacy score and time (self-efficacy score x time) will also be included. We expect the interaction term coefficient (group x time) in model for H1 will be significant, and the coefficient of the interaction term between group and time (group x time) will be attenuated and may become non-significant after extending the model to add total self-efficacy score as a covariate and the interaction between total self-efficacy score and time (total self-efficacy score x time). This will indicate that the self-efficacy has a mediated effect on the association between the intervention and change in the primary outcome (RMBPC reactivity score ⁽²⁾) as compared to the control group. We will also extend these models to include diagnosis, frequency of behavioral symptoms as measured on the RMBPC ⁽²⁾, socio-demographic covariates and preparedness (78). All of results above will be considered significant at $\alpha = 0.05$, with two-sided tests.

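### Both arms are treated in live session groups of up to 8, but the H1, H2 and H4 models carry only a subject random intercept, so type I error in H1 and H2 exceeds 0.05 if change correlates within session groups

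*Combined protocol and SAP*

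**What the plan says.** In this note, arm means the randomised group (test or control) and session group means the set of care partners who meet together on video.

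- **Allocation is individual.** Section 6, Randomization: "Care partners will be randomized to either the test or control group".
- **Delivery is in groups, in both arms.** Section 4 describes the intervention as "delivered in a peer environment via videoconferencing technology". Section 6 (Interventionists; The Intervention) sets eight weekly live sessions, no more than eight care partners per session group, and two guides for each.
- **Peer influence is intended.** The basic curriculum, given to both arms, has guides promote exchange between members. In the test arm, learning from peers is one of four stated routes to self-efficacy. Section 9 calls peer support a key element.
- **Guides differ by arm.** Section 4, Rigor, bias and transparency: "We will engage separate interventionists and handbooks for each group".
- **The H1 model** (Section 8, Aim 1) asks whether change in RMBPC reactivity "differs across groups (test vs. control) over the intervention period". It tests arm by time, and its random part is "Random intercepts will be incorporated for subject specificity in the model to account for clustering effect within subject over time".
- **H2:** "we will employ a similar mixed effect model as H1". Its random effects are not restated, so the subject-only structure is inferred.
- **H4** extends the H1 model and looks at whether the arm-by-time coefficient "may become non-significant after extending the model to add total self-efficacy score as a covariate".
- **Sample size** (Section 4): "we need at least 117 to 128 subjects/each group, for alpha = 0.05". The ICC of 0.5 to 0.6 used there is the correlation between repeated measures on one person.

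Session group, cohort and guide appear nowhere as a random effect, a covariate, a robust-variance cluster or a design effect.

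**The concern.** People who share eight weeks of sessions, guides and peers may improve, or fail to improve, together. A subject intercept absorbs stable differences between people. It does not absorb a shared session-group effect on change, and change is what the arm-by-time coefficient measures. With positive correlation of change, 128 people in an arm carry less information than the model credits them with. The standard error is then too small, and the nominal 0.05 tests in H1 (primary) and H2 reject too often. The same understated standard error enters H4, where the arm-by-time coefficient is read for attenuation or loss of significance. The stated power also makes no allowance for session groups.

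**Working it through.** **1. Inputs.** From the documents: two-sided alpha 0.05, 80% power, standardised effect 0.3, three repeated measures, within-subject ICC 0.5 to 0.6, session groups of up to 8, 300 care partners enrolled (150 per arm if split equally), up to 15% attrition. Session groups per arm: 128/8 = 16 at least for those analysed; 150/8 = 18.75, so 19 for those enrolled. Assumed, because the documents give no value: session-group ICC (the share of variance in pre-post change that lies between session groups) of 0.01, 0.02, 0.05 or 0.10, equal in both arms unless stated.

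**2. The plan's own figure.** n per arm = 2 × (1.96 + 0.8416)² × (1 + 2ρ) / (3 × 0.3²).
- ρ = 0.5: 116.3, so 117.
- ρ = 0.6: 127.9, so 128.

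Both stated figures reproduce with within-subject correlation alone, so they contain no session-group term. This formula is for a time-averaged difference, whereas H1 tests arm by time.

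**3. Formulas with session groups of 8.** Design effect DE = 1 + 7 × ICC. Actual type I error = 2 × (1 − Φ(1.96/√DE)). Effective n = 128/DE. Power, taking the plan's 80% as the start = Φ(2.8016/√DE − 1.96).

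**4. Simulation of the planned test.** Random-intercept model, continuous time, arm by time; no true arm effect; 16 groups of 8 per arm; weeks 4, 8 and 12; complete visits. The main run had 20,000 trials per setting, within-subject ICC 0.55, and a session-group effect growing from 0 at week 4 to its full size at week 12. The H1 ranges below span this run and repeats with small differences in set-up. Week 12 for the first post-assessment is inferred: Weeks 20 and 36 are 2 and 6 months after the sessions end. H2 uses weeks 4 and 12 because self-efficacy is not measured at week 8 (Table 3).

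| Assumed session-group ICC | 0.01 | 0.02 | 0.05 | 0.10 |
|---|---|---|---|---|
| Design effect | 1.07 | 1.14 | 1.35 | 1.70 |
| Type I error, formula | 0.058 | 0.066 | 0.092 | 0.133 |
| Type I error, H1 simulated | 0.056-0.060 | 0.066-0.071 | 0.093-0.099 | 0.140-0.149 |
| Type I error, H2 simulated | 0.057 | 0.065 | 0.092 | 0.130 |
| H1, clustering in test arm only | 0.055 | 0.059 | 0.074 | 0.100 |
| H1, 26 groups of 5 per arm | 0.053 | 0.061 | 0.074 | 0.106 |
| H1, 150 per arm in 19 groups, 15% attrition | 0.058 | 0.064 | 0.084 | 0.125 |
| Effective n per arm (from 128) | 120 | 112 | 95 | 75 |
| Power by the plan's formula | 77% | 75% | 67% | 58% |

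**5. Checks on the condition.** With session-group ICC 0, simulated type I error was 0.048-0.051. With a session-group effect that is constant over time it was 0.048-0.052. So only correlation of change does harm. Part of the excess of simulation over formula comes from the missing random slope and not from clustering: with groups of size 1 and ICC 0.10, type I error was 0.055.

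**6. Does the remedy work?** With independent session groups, cluster-robust errors with a small-sample correction and t on (number of session groups − 2) degrees of freedom, here 32 − 2 = 30, held type I error at 0.046-0.053. A random session-group-by-time effect gave 0.031-0.051 and is conservative when the ICC is near zero. If half the session-group variance comes from guides and only four guide pairs serve each arm (both assumptions), the cluster-robust option gives 0.061 at ICC 0.01, 0.074-0.079 at 0.02, 0.098-0.104 at 0.05 and 0.139-0.144 at 0.10.

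**The case against.** **The size is assumed.** The documents give no session-group ICC, and standardised guide training and fidelity review may keep guide-related correlation low. This stands as to size: at 0.01-0.02 the excess is minor. It does not remove correlation from shared peers, which the design sets out to create. The simulations also use the unadjusted model; whether the planned covariates would reduce the correlation was not examined.

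**The trial is Stage 1B.** It tests preliminary efficacy and feeds a later study, which limits the consequence. The plan nevertheless sets a two-sided 0.05 test and says that the design will provide evidence for efficacy.

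**There is spare power.** Section 4 expects extra power from conservative inputs, but assigns it to covariate adjustment. Extra power does not correct type I error.

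**Stronger readings that the documents do not support.**
- A reader might infer that the primary test is inflated as a fact. It is inflated only if change correlates positively within session groups.
- A reader might take larger figures from a model that also includes week 1 (0.057/0.074/0.108/0.169 for H1 at the four ICC values). Section 8 does not list the visits, but it refers to the intervention period, the sample size rests on three measurements, and week 1 serves the separate pre-intervention check. That is a secondary reading.
- A reader might infer an inflated mediation test in H4. H4 defines no formal mediation test; the consequence there is only an understated standard error.
- A reader might infer that clustering by session group secures the error rate. It does so only if session groups are independent. The number of guides is not given, so guides may lead several groups.

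**Conclusion.** The omission is clear. Treatment is delivered in interacting groups in both arms, and neither the H1 model, the H2 model inferred from it, the H4 extension nor the sample size allows for that. The direction is certain for any positive within-group correlation of change; the amount is not known. With 16 groups of 8 per arm, both arms clustered and weeks 4, 8 and 12, type I error would be about 0.06, 0.07, 0.09-0.10 and 0.14-0.15 at session-group ICC 0.01, 0.02, 0.05 and 0.10. It is lower with smaller groups or with clustering in one arm only. The excess becomes material from about 0.05. The fall from 80% power is measured on the plan's own time-averaged formula with 128 analysed per arm, so it is not the power of the arm-by-time test itself. This should be corrected before the data are analysed. It does not show that the trial cannot answer its question.

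**What to change.** - **Record** each participant's session group, or that none was joined, and the guides who led it.
- **Prespecify** for H1, H2 and H4, and for the corresponding Week 20 and Week 36 analyses, one of two options: (a) session group nested in arm with a random session-group-by-time effect; or (b) cluster-robust standard errors by session group with a small-sample correction. In both, base the degrees of freedom on the number of session groups formed. Apply the same clustering to H3 for consistency. A session-group intercept alone is not enough, because the test is on change.
- **Participants who never join a session group** count as their own cluster.
- **Shared guides.** If guides lead several groups, add a guide-by-time random effect or cluster by guide pair as a sensitivity analysis. State that guide effects cannot be fully separated from arm, because guides are separate by arm. Neither option solves that.
- **Restate power** over an assumed range of session-group ICC and group size, without enrolling more.

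Cost: SAP wording and two recorded variables, with no new outcome data and no added enrolment. Intervals will be wider and stated power lower. Some power is lost even if the ICC is zero: with the planned test set to 80% in simulation, about three percentage points under (b) and six under (a).

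### The H1 and H2 models specify only a random intercept; if correlation between visits decays, the group x time test is mildly anti-conservative at end of intervention and more so at weeks 20 and 36

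*Combined protocol and SAP*

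**What the plan says.** Section 8 (Data Analysis), Aim 1, H1 sets out a mixed model for RMBPC reactivity with group, time as a continuous variable, and group x time. The interaction coefficient is tested two-sided at 0.05. On dependence within a person the text says only: "Random intercepts will be incorporated for subject specificity in the model to account for clustering effect within subject over time". It then adds: "Similar analyses will occur at Week 20 and 36".

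H2 applies a model of the same kind to total self-efficacy. H3 repeats the random-intercept statement, and H4 extends the H1 model.

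The sample size paragraph in section 4 makes the same assumption: "three repeated measurements and an Intra-Class Correlation (ICC) =0.5 to 0.6 in compound symmetry covariance structure".

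Neither section 4 nor section 8 mentions a random slope, a serial or unstructured residual covariance, robust standard errors, or a check of the covariance structure.

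The visits are unequally spaced. Table 3 labels weeks 1, 4 and 8, and the H1 text names weeks 20 and 36. Week 12 for Post Assessment 1 is inferred from the length of the intervention. Table 3 lists only the RMBPC at week 8, so self-efficacy has no value at that visit.

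**The concern.** With a random intercept and independent residuals, the model gives weeks 1 and 4 the same correlation as weeks 1 and 36. A group x time coefficient in linear time draws most of its information from the earliest and latest visits. If those visits are less correlated than the average pair, the true variance of the slope difference exceeds the variance the model reports. The standard error and confidence interval are then too small, and the test rejects too often under the null.

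Decay is plausible here. The Background (section 3) says behavioral symptoms grow with progression and appear at different phases in different subtypes, and all subtypes are enrolled together. Care partners may therefore differ in their rate of change, which a random intercept cannot represent. At stake are the stated error rate for H1 and H2 and the width of the intervals behind any claim of durability at weeks 20 and 36.

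**Working it through.** **The plan's own figure.** The plan states: "we need at least 117 to 128 subjects/each group, for alpha = 0.05". With effect size 0.3, 80% power, two-sided 0.05 and m = 3 measurements, n per group = 2(1.960 + 0.842)²/0.3² × (1 + 2·ICC)/3. This gives 116.3, rounded up to 117, at ICC 0.5, and 127.9, rounded up to 128, at ICC 0.6. Both match. This is the formula for a time-averaged difference under compound symmetry. It confirms the covariance assumption but says nothing about decay.

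**Variance of the tested coefficient.** Take complete data, unit variance, visit times t, c = t − mean(t), Sxx = c'c and true correlation matrix R. The random-intercept estimate of group x time is the difference in mean within-person slopes.

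- Model variance: (2/n) × σw²/Sxx, where σw² = 1 − the average pairwise correlation.
- True variance: (2/n) × c'Rc/Sxx².
- Variance ratio: VR = c'Rc/(Sxx × σw²).
- Actual type I error: 2Φ(−1.96/√VR).

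The per-group n cancels from the ratio.

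**Assumed decay (not from the documents).** Correlation at distance d weeks is A·exp(−kd), set to 0.60 or 0.70 at 4 weeks and 0.40 or 0.50 at 35 weeks. All four combinations were computed.

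**Worked corners, weeks 1, 4, 8, 12, 20, 36** (mean 13.5, Sxx = 827.5):

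- 0.70 falling to 0.40: k = ln(0.70/0.40)/31 = 0.01805 and A = 0.752. c'Rc = 616.0 and σw² = 0.418. VR = 616.0/(827.5 × 0.418) = 1.78, √VR = 1.33, type I error 14.2%.
- 0.60 falling to 0.50: c'Rc = 451.9 and σw² = 0.437. VR = 451.9/(827.5 × 0.437) = 1.25, √VR = 1.12, type I error 8.0%.

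**Range over the four combinations:**

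| Visits used | Type I error at nominal 5% |
|---|---|
| 4, 8, 12 | 5.3-6.2% |
| 1, 4, 8, 12 | 5.7-7.9% |
| 1 through 20, all visits | 6.4-10.4% |
| 1 through 36, all visits | 8.0-14.2% |
| 4, 12, 20 only | 5.5-6.8% |
| 4, 12, 36 only | 6.1-8.3% |
| H2: 4, 12 only | 5.0% |
| H2: 1, 4, 12, 20, 36 | 7.5-12.5% |

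With two visits there is a single pairwise correlation, so the model cannot get it wrong.

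**Checks.** Under true compound symmetry the formula gives 5.0% at every horizon. Null simulations (8,000 replicates, 128 per group, complete data) used a steeper assumed decay, pure exponential with 8-week correlation 0.7. They gave 10.0%, 16.6%, 19.0% and 21.3% for the first four rows, against 10.2%, 15.9%, 19.2% and 21.8% from the formula. On simulated data with decaying correlation, a test on each person's own slope, which with complete data corresponds to adding a random slope, held 4.7-5.4%. Sandwich standard errors were tried in one scenario (weeks 4, 8, 12; 15% dropout; 500 replicates) and gave 4.6%, against 9.8% for the random-intercept model. The unstructured option was not simulated.

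**The case against.** The strongest reply is that decay is assumed. The only correlation in the documents is an ICC of 0.5 to 0.6 under "compound symmetry covariance structure", and the outcome is the care partner's reaction, not the patient's severity. That stands: the direction is secure given decay, but its size is not documented.

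Second, H1 is framed over the intervention period. Read as weeks 4, 8 and 12, the inflation is about 5-6%. The 6-8% figure needs week 1, which the plan uses for the separate pre-intervention stability check. The text does not exclude week 1 from H1, so both readings remain open.

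Third, the plan does not say which visits enter the week 20 and 36 analyses. If only weeks 4 and 12 plus the later visit are used, the error is about 6-8%. This also stands.

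Fourth, a random intercept does not logically rule out a correlated residual. That is true, but none is named and the power section assumes equal correlation.

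A reader might infer that the 0.05 level for the primary outcome simply fails, or point to error rates up to 26% through week 36. The documents do not support either reading. The first depends on decay and on which visits are used. The second comes from steeper decay rates (8-week correlations of 0.5 to 0.9), which are also assumptions.

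**Conclusion.** The concern holds conditionally. As written, H1 and, by reference, H2 assume equal correlation across unequally spaced visits and offer no protection if that is wrong. Under the assumed decay and complete data, the end-of-intervention test is only mildly affected. The week 20 and 36 analyses are the most exposed, above all if all earlier visits are pooled: the week-36 variance ratio is then 1.25-1.78, so the reported standard error is about 11-25% too small (1 − 1/√1.25 to 1 − 1/√1.78). If correlation is in fact equal, or if only two visits are used, there is no inflation. The H3 and H4 tests have self-efficacy as a predictor and were not computed, so no size is claimed for them. This is an inexpensive improvement to make before analysis; it does not show that the primary result would be invalid.

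**What to change.** In H1 and H2, including the week 20 and 36 analyses, replace the random-intercept-only structure by one that does not force equal correlation. Either a random slope for time or an unstructured within-person covariance would do (six visits give 6 × 7/2 = 21 parameters, with 300 care partners planned). Alternatively, keep the random intercept and use robust (sandwich) standard errors. Name the choice and a fallback for non-convergence in advance, and list the visits that enter each analysis. Use the same structure in H3 and H4 for consistency.

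The cost is SAP wording and one model option. For the same slope estimate, intervals on weeks 4, 8 and 12 widen by about 1-5% (√1.023 to √1.103). Through week 36, with all visits, they widen by about 12-33% (√1.25 to √1.78). Nominal power falls to match: an effect sized for 80% power under the random-intercept standard error would have about 71% (Φ(2.80/1.118 − 1.96)) to 56% (Φ(2.80/1.334 − 1.96)). An unstructured covariance reweights the visits, and its width was not computed.
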